1.5 Paricalcitol (Zemplar®)

Refer to Appendix 2- Package Insert for Paricalcitol for complete information.

Paricalcitol is a vitamin D analog used for the prevention and treatment of secondary hyperparathyroidism. Excessive amounts of vitamin D compounds including paricalcitol can cause over suppression of the parathyroid hormone, hypercalcemia, hypercalciuria, hyperphosphatemia and adynamic bone disease.

Paricalcitol should not be given to patients with evidence of vitamin D toxicity, hypercalcemia, or hypersensitivity to any ingredient in this product.

The most common side effects of treatment with paricalcitol are diarrhea, nasopharyngitis, dizziness, vomiting, hypertension, hypersensitivity, nausea and edema.

Taste perversion, such as metallic taste, and allergic reactions, such as rash, urticaria and pruritus rarely have been reported.

Risks associated with treatment with paricalcitol include: Symptoms of elevated calcium levels e.g. feeling tired, difficulty in thinking clearly, loss of appetite, nausea, vomiting, constipation, increased thirst, increased urination and weight loss. Prescription based doses of vitamin D should be withheld during treatment with paricalcitol.

The effects of paricalcitol on unborn fetus and possible transmission through breast milk have not been fully established. Patients on paricalcitol should avoid pregnancy and should not breast feed.

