AEs associated with pembrolizumab exposure may represent an immunologic etiology. These immune-related AEs (irAEs) may occur shortly after the first dose or several months after the last dose of pembrolizumab treatment and may affect more than one body system simultaneously. Therefore, early recognition and initiation of treatment is critical to reduce complications. Based on existing clinical study data, most irAEs were reversible and could be managed with interruptions of pembrolizumab, administration of corticosteroids and/or other supportive care. For suspected irAEs, ensure adequate evaluation to confirm etiology or exclude other causes. Additional procedures or tests such as bronchoscopy, endoscopy, skin biopsy may be included as part of the evaluation. Based on the severity of irAEs, withhold or permanently discontinue pembrolizumab and administer corticosteroids. Dose modification and toxicity management guidelines for irAEs associated with pembrolizumab are provided in Table 4.

Table 4. Dose Modification and Management Guidelines for Drug-Related Adverse Events

| General instructions: | | | | |
|---|--|--------------------------------------|---|---|
| 
 1. Corticosteroid taper should be initiated upon AE improving to Grade 1 or less and continue to taper over at least 4 weeks. 2. For situations where pembrolizumab has been withheld, pembrolizumab can be resumed after AE has been reduced to Grade 1 or 0 and corticosteroid has been tapered. Pembrolizumab should be permanently discontinued if AE does not resolve within 12 weeks of last dose or corticosteroids cannot be reduced to ≤ 10 mg prednisone or equivalent per day within 12 weeks. 3. For severe and life-threatening irAEs, IV corticosteroid should be initiated first followed by oral steroid. Other immunosuppressive treatment should be initiated if irAEs cannot be controlled by corticosteroids. | | | | |
| irAEs | Toxicity grade or conditions (NCI CTCAE v4.0) | Action taken to pembrolizumab | irAE management with corticosteroid and/or other therapies | Monitor and follow-up |

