- r. For only those patients consenting to the optional tumor biopsy, a baseline tumor biopsy will be collected and used for profiling. If possible (patient condition permitting) this will be repeated after 9 ± 1 weeks on trial treatment, or at the time of disease progression. (Refer to 6.1.2.8).

Table 8. Post-Treatment Period (EOT– Follow-Up) Schedule

| Post-Treatment Period | Scheduling Window (Days) | | |
|--|--|----------------------|---|
| | EOT | 30 days from EOT | Every 90 days post EOT |
| | At time of discontinuation (within 5 days of last dose) | 30 ± 5 days from EOT | 90 ± 5 days from EOT then every 90 ± 15 days ⁱ |
| Post-trial anticancer treatment status | X | X | X |
| Disease/Survival Status ^a | X | X | X |
| Concomitant Medication Review | X | X | X |
| Assess & Report Adverse Events ^b | X | X | X |
| Directed Physical Examination | X | | |
| Patient Personalized Clinical Benefit App | X | | |
| Vital Signs and Weight ^c | X | | |
| ECG | X | | |
| ECOG (see appendix 4) | X | | |
| Serum β HCG Pregnancy Test for WOCBP | X | X | |
| CBC with Differential | X | | |
| Comprehensive Serum Chemistry Panel | X | | |
| Urinalysis | X | | |
| T3, FT4 and TSH | X | | |
| Tumor Imaging ^d | X | | |
| CA19-9 ^e | X | | |
| Central Lab Samples (Blood and Fecal Swab ^f) | X | X ^f | |
| Review contraception use as required by protocol Section 4.7.2 (where applicable) ^g | X | X | X |
| Optional -Tumor Tissue Collection | [Tumor tissue collection for those that consent to this optional collection and undergo a routine care biopsy of their tumor during their participation in the study] ^j | | |
| Contact Information Review ^h | X | X | X |

Footnotes for Table 8. Post –Treatment Period

a. Post-treatment follow-up for disease status until documented disease progression, initiating a non-trial cancer treatment, withdrawing consent or becoming lost to follow-up. After documented disease progression each pt will be followed by telephone for survival status.

b. Assess and record any new or ongoing AEs at time of EOT. Following the EOT, each patient will be followed for 30 days, for adverse event monitoring. Serious adverse events and Events of Clinical Interest (ECI) will be collected for 90 days after the end of treatment as described in Section 6.2.3.1.

c. Vital signs to include: Blood pressure, pulse, respiratory rate, and temperature.

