6.1.3 Laboratory Procedures/Assessments

Safety laboratory tests for hematology, chemistry, and urinalysis (as detailed in Table 9) will be performed by the local laboratory for each investigational site at screening, baseline and throughout the trial treatment period. Serum vitamin D levels will be performed at screening. HBsAg and HCV RNA (qualitative) will be performed at screening if not performed within the last 3 months. Thyroid and Parathyroid function (T3, FT4 TSH, and PTH) will be performed as part of screening and every other cycle during the trial treatment period.

Table 9. Laboratory Tests – performed locally

| Hematology | Chemistry | Urinalysis | Other |
|------------------------------|----------------------------------|---|--|
| Hematocrit | Albumin | Blood | Serum β -human chorionic gonadotropin† |
| Hemoglobin | Alkaline phosphatase | Glucose | PT (INR) |
| Platelet count | Alanine aminotransferase (ALT) | Protein | aPTT |
| WBC (total and differential) | Aspartate aminotransferase (AST) | Specific gravity | Thyroid stimulating hormone (TSH) |
| Red Blood Cell Count | Lactate dehydrogenase (LDH) | Microscopic exam (If abnormal results are noted) | Total triiodothyronine (T3) |
| Absolute Neutrophil Count | Carbon Dioxide ‡ | | Free thyroxine (T4) |
| Absolute Lymphocyte Count | (CO ₂ or bicarbonate) | | PTH (parathyroid hormone) |
| | Uric Acid | | Serum vitamin D (25- |

| Hematology | Chemistry | Urinalysis | Other |
|--|--|------------|---------------------|
| | | | hydroxy vitamin D) |
| | Calcium | | HBsAG |
| | Chloride | | HCV RNA qualitative |
| | Glucose | | |
| | Phosphorus | | |
| | Potassium | | |
| | Sodium | | |
| | Magnesium | | |
| | Total Bilirubin | | |
| | Direct Bilirubin (If total bilirubin is elevated above the upper limit of normal) | | |
| | Total protein | | |
| | Blood Urea Nitrogen | | |
| | Creatinine | | |
| † Perform on women of childbearing potential (WOCBP) only. | | | |
| ‡ If considered standard of care in your region. | | | |

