6.2.3.2 Events of Clinical Interest (ECI)

Selected non-serious and serious adverse events are also known as Events of Clinical Interest (ECI) and must be reported within 24 hours to the Sponsor and the Sponsor will report within 24 hours (working days) to Merck Global Safety.

Events of clinical interest for this trial include:

1. An overdose of pembrolizumab, as defined in Pharmacy manual and Section 6.2.1 - Definition of an Overdose for This Protocol and Reporting of Overdose, that is not associated with clinical symptoms or abnormal laboratory results.
2. An elevated AST or ALT lab value that is greater than or equal to 3X the upper limit of normal and an elevated total bilirubin lab value that is greater than or equal to 2X the upper limit of normal and, at the same time, an alkaline phosphatase lab value that is less than 2X the upper limit of normal, as determined by way of protocol-specified laboratory testing or unscheduled laboratory testing. *

*Note: These criteria are based upon available regulatory guidance documents. The purpose of the criteria is to specify a threshold of abnormal hepatic tests that may require an additional evaluation for an underlying etiology.

For the time period beginning when the consent form is signed until treatment allocation/randomization, any ECI, or follow up to an ECI, that occurs to any patient must be reported within 24 hours to the Sponsor and the Sponsor will report within 24 hours (working days) to Merck Global Safety if it causes the patient to be excluded from the trial, or is the result of a protocol-specified intervention, including but not limited to washout or discontinuation of usual therapy, diet, placebo treatment or a procedure.

For the time period beginning at treatment allocation/randomization through 90 days following cessation of treatment, or 30 days following cessation of treatment if the patient initiates new anticancer therapy, whichever is earlier, any ECI, or follow up to an ECI, whether or not related to pembrolizumab, must be reported within 24 hours to the Sponsor and the Sponsor will report within 24 hours (working days) to Merck Global Safety.

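### After the EOT visit no chemistry, CBC or thyroid test is scheduled, so a hepatic ECI defined only by laboratory values and reportable for up to 90 days is ascertained passively

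*Protocol*

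**What the plan says.** **Event and window.** Protocol 6.2.3.2 defines the second ECI by liver tests alone. It begins "An elevated AST or ALT lab value that is greater than or equal to 3X the upper limit of normal" and also requires raised total bilirubin and an alkaline phosphatase below a set limit, "as determined by way of protocol-specified laboratory testing or unscheduled laboratory testing". The main window is given by "For the time period beginning at treatment allocation/randomization through 90 days following cessation of treatment", cut to 30 days if new anticancer therapy starts sooner. Within it, "any ECI, or follow up to an ECI, whether or not related to pembrolizumab, must be reported within 24 hours to the Sponsor". Table 8, footnote b, repeats the 90 days.

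**Tests after treatment.** Table 8 (Protocol 5.0) shows "Comprehensive Serum Chemistry Panel | X" under EOT and nothing under the 30-day or 90-day columns. The rows for CBC, urinalysis and thyroid tests follow the same pattern. The 30-day list in 6.1.7.4 contains one blood test, the serum pregnancy test for women of childbearing potential (WOCBP). The central-sample row is marked at 30 days, but its footnote covers the fecal swab only. The 90-day contact is by telephone.

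**Expected timing of toxicity.** Protocol 4.2.4 says that immune-related events "may occur shortly after the first dose or several months after the last dose of pembrolizumab treatment".

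**PTH.** Protocol 6.1.3 states: "Thyroid and Parathyroid function (T3, FT4 TSH, and PTH) will be performed as part of screening and every other cycle". PTH is absent from EOT in both Table 8 and 6.1.7.3, where the thyroid tests remain.

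**Analysis window.** SAP section 5 runs the toxicity endpoint from first treatment to end of treatment. SAP 7.1 and Protocol 8.3.5.1 summarise events from Cycle 1 Day 1 and give no end date.

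**The concern.** On treatment, 6.1.7.2 draws chemistry on Days 1, 8 and 15 of each cycle. After EOT the schedule goes from roughly weekly to none, while the duty to report a laboratory-defined event continues. The protocol names hepatitis and thyroid disorders as pembrolizumab risks (1.4) and expects some immune events late.

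Toxicity by arm is the first secondary objective. ECIs are tabulated, and SAP 7.1 compares the proportions with toxicity. With 12 patients per arm, one patient is 1/12 = 8.3% of an arm, so a single missed event is visible in the table. A report of no late hepatic ECIs could not fully separate absence of events from absence of testing. If the SAP section 5 window is applied literally, late events that are found may also be left out of the tabulation.

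**Working it through.** The plan states no figure on this point, so there is none to reproduce. The check sets the reporting rule against the schedule and counts days.

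**Inputs**
- ECI window: 90 days after cessation of treatment, or 30 with new anticancer therapy (6.2.3.2).
- EOT visit: day 0 to 5 after the last dose of trial treatment (Table 8, 6.1.7.3).
- Chemistry after EOT: none scheduled (Table 8, 6.1.7.4).
- 30-day visit: 30 ± 5 days after the last dose (6.1.7.4).
- Last paricalcitol or placebo dose in a cycle: Day 19, +1 day; pembrolizumab on Day 1 (4.2.6).
- PTH: screening, then before cycles 3, 5, 7 and so on (Table 7, footnote i).

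**Days in the ECI window with no scheduled liver test** = window − EOT day
- 90-day window: 90 − 5 = 85 to 90 − 0 = 90 days (94% to 100%).
- 30-day window: 30 − 5 = 25 to 30 − 0 = 30 days (83% to 100%).

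**EOT relative to pembrolizumab.** EOT is timed from the last dose of any trial treatment. If that is paricalcitol or placebo on Day 20, EOT can fall on Day 25, which is 25 − 1 = 24 days after the last pembrolizumab infusion. For some patients, then, the EOT panel is itself a fairly late look at pembrolizumab toxicity. It does not shorten the untested part of the ECI window if cessation is counted from the last dose of either drug.

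**What a draw at the 30-day visit would change.** It gives one look in a window that now has none. After it, 90 − 30 = 60 days remain without a scheduled test (90 − 35 = 55 to 90 − 25 = 65 with the visit window).

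**PTH.** Take a patient who stops late in an even-numbered cycle, an illustrative assumption. The last scheduled PTH is at the start of the preceding cycle, so the gap to EOT is 21 + 20 + 5 − 1 = 45 days. With a 3-day cycle slip and the 72-hour pre-dose allowance it is 24 + 20 + 5 − 1 + 3 = 51 days.

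**The case against.** **The passages can both be followed.** A duty to report known events does not oblige the sponsor to schedule tests for them. This is fair: it is a mismatch of purpose and not a logical contradiction.

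**Late events can still be found.** A reader might infer that they cannot be detected at all. The documents do not support that. Unscheduled tests count towards the ECI, and 6.1 allows investigators to perform procedures off schedule and the sponsor to require safety testing. Grade > 1 events are followed (6.1.7.4), and Table 4 calls for liver-test monitoring once an elevation is known. Adverse events are reviewed at the 30-day visit and the 90-day contact. An event severe enough to raise bilirubin may also show symptoms listed in 1.4, such as jaundice. What remains is that these routes need a symptom, a known abnormality or a discretionary order, and a new symptomless abnormality supplies none of them.

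**Bias between arms.** A reader might infer that the toxicity comparison is biased. That is not shown: both arms receive pembrolizumab and share one schedule. Protocol 6.1.6.2 lets the treating investigator learn the assignment at progression, so discretionary testing could be ordered by someone who knows the arm. That is a possibility only.

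**One draw does not cover 90 days.** Correct, as the working shows. For a patient who starts new therapy early, the 30-day visit is brought forward and the draw adds less.

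**PTH is a side issue.** It has no part in the ECI, and calcium and phosphorus are already in the EOT chemistry panel. Patients treated through a confirmatory scan 4 to 6 weeks after a week-9 progression reach days 63 + 28 = 91 to 63 + 42 = 105, past cycle 5 Day 1 (day 1 + 4 × 21 = 85), and so have a second on-treatment PTH. The point stands only as a small one.

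**Conclusion.** The point holds as one of passive ascertainment. After EOT, new symptomless hepatic or thyroid abnormalities are not systematically looked for, although the protocol expects late immune events and keeps a laboratory-defined ECI reportable. Of the 90-day window, 85 to 90 days have no scheduled liver test; of the 30-day window, 25 to 30 days. The day counts assume that cessation means the last dose of trial treatment and that EOT falls within its 5 days. How many events would be missed cannot be estimated from the documents. The conclusion extends neither to impossibility of detection nor to a demonstrated difference between arms.

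Two related points also stand. The SAP toxicity window does not match the collection windows or the open-ended analysis text. Separately, and of less weight, PTH has no end-of-exposure value although 1.5 warns: "Excessive amounts of vitamin D compounds including paricalcitol can cause over suppression of the parathyroid hormone, hypercalcemia".

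**What to change.** - **Schedule.** Reconcile Table 8, 6.1.7.4 and 6.2.3.2 by adding the existing Table 9 chemistry panel and thyroid tests to the mandatory 30-day safety visit. Cost: one local blood draw per patient, about 24 in all, at a visit already made in person.
- **Reporting.** State in the study report that laboratory ECIs after that visit are passively ascertained. If no test is added, say the same for the whole period after EOT.
- **SAP.** Give the toxicity endpoint in section 5 an end date that matches the 30-day (all adverse events) and 90-day (serious events and ECIs) collection periods, including the 30-day cut for new therapy. Align SAP 7.1 and Protocol 8.3.5.1 so that post-EOT events are tabulated. Cost: a text change.
- **PTH.** Add it to the EOT blood draw in Table 8 and 6.1.7.3, so that each arm has an end-of-exposure value. Cost: one assay on blood already being drawn.

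A minor amendment covers all of this. It concerns outcome ascertainment and sets no dose, stopping or treatment rule.

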6.0 TRIAL PROCEDURES

6.1 Trial Procedures

Individual trial procedures (Administrative, Clinical, and Laboratory) are described in detail below. The specific visit requirements are detailed in Section 6.1.7. It may be necessary to perform these procedures at unscheduled time points if deemed clinically necessary by the investigator.

Furthermore, additional evaluations/ testing may be deemed necessary by the Sponsor for reasons related to patient safety. In some cases, such evaluation/testing may be potentially sensitive in nature (e.g., HIV, Hepatitis C, etc.), and thus local regulations may require that additional informed consent be obtained from the patient. In these cases, such evaluations/testing will be performed in accordance with those regulations.

6.1.1 Administrative Procedures

6.1.1.1 *Informed Consent*

The Investigator or qualified designee must obtain documented consent from each potential patient prior to participating in a clinical trial.

6.1.1.1.1 *General Informed Consent*

Consent must be documented by the patient's dated signature. A copy of the signed and dated consent form should be given to the patient before participation in the trial.

The initial informed consent form, any subsequent revised written informed consent form and any written information provided to the patient must receive the IRB/ERC's approval/favorable opinion in advance of use. The patient or his/her legally acceptable representative should be informed in a timely manner if new information becomes available that may be relevant to the patient's willingness to continue participation in the trial. The communication of this information will be provided and documented via a revised consent form or addendum to the original consent form that captures the patient's dated signature or by the patient's legally acceptable representative's dated signature.

The informed consent will adhere to IRB/ERC requirements, applicable laws and regulations and Sponsor requirements.

6.1.1.2 Inclusion/Exclusion Criteria

All inclusion and exclusion criteria will be reviewed and documented by the investigator or qualified designee to ensure that the patient qualifies for the trial.

6.1.1.3 Medical History

A medical history will be obtained by the investigator or qualified designee. Medical history will include all active conditions, and any condition diagnosed within the prior 10 years that are considered to be clinically significant by the Investigator. Details regarding the disease for which the patient has enrolled in this trial will be recorded separately and not listed as medical history.

6.1.1.4 Prior and Concomitant Medications Review

6.1.1.4.1 Prior Medications

The investigator or qualified designee will review prior medication use, including any protocol-specified washout requirement, and record prior medication taken by the patient within the 30 days before starting the trial. Treatment for the disease for which the patient has enrolled in this trial will be recorded separately and not listed as a prior medication.

6.1.1.4.2 Concomitant Medications

The investigator or qualified designee will record medications including prescription, over-the-counter (OTC), multivitamins, nutritional and/or herbal supplements, IV medications and fluids, if any, taken by the patient during the trial. All medications related to reportable SAEs and Events of Clinical Interest (ECIs) should be recorded as defined in Section 6.2.

6.1.1.5 Disease Details and Treatments

6.1.1.5.1 Disease Details

The investigator or qualified designee will obtain prior and current details regarding disease status.

6.1.1.5.2 Prior Treatment Details

The investigator or qualified designee will review all prior cancer treatments including systemic treatments, radiation and surgeries. The investigator will assess and provide as part of the baseline eCRF data, the Best Response on the last treatment prior to enrollment in this trial.

6.1.1.5.3 Subsequent Anti-Cancer Therapy Status

The investigator or qualified designee will review all new anti-neoplastic therapy initiated after the last dose of trial treatment. If a patient initiates a new anti-cancer therapy within 30 days after the last dose of trial treatment, the EOT visit must occur before the first dose of the new therapy. Once new anti-cancer therapy has been initiated the patient will move into survival follow-up.

6.1.1.6 Assignment of Screening Number

A patient will be assigned a screening number once they provide written informed consent for the trial. This screening number will be site specific and maintained on a Screening log in the Investigator Site File.

6.1.1.7 Assignment of Randomization Number

Eligible patients will be assigned a randomization number that will serve as the patient's number throughout the trial. This randomization number will be maintained on a Randomization log in the Investigator Site File.

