4.3 Randomization or Treatment Allocation

Randomization will be in a 1:1 ratio to pembrolizumab + paricalcitol or pembrolizumab + placebo. Randomization will be performed by the trial biostatistician or designee using a computer-generated algorithm with a block size of 4. The RAND function in MySQL is used to generate a random number, with a value based on the computer clock used as seed. The program randomly assigns participants to one of the two treatments with the pre-selected block size. After study initiation, the randomization sequence will be provided to the unblinded central monitor. After consent and confirmation of eligibility, the site study coordinator will notify the site pharmacist and the unblinded monitor. The unblinded monitor will provide the next randomized treatment from the sequence to the site pharmacist. The unblinded monitor also will notify the trial biostatistician. The trial biostatistician or designee will be available to assist with identifying the next randomized treatment if the unblinded central monitor is not available.

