4.4 Stratification

No stratification will be performed.

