Fecal samples will be collected by the patient at home during trial participation. Patients will be asked to collect two samples per treatment cycle. One fecal swab sample is to be collected within the 72 hours prior to Day 1 of each treatment cycle, and a second fecal swab sample within 24-72 hours after treatment on Day 1. The patient will also be asked to collect one final sample approximately 30 days following treatment discontinuation. Patients will be provided with collection instructions (refer to Appendix 9), collection container, sterile CultureSwabs in individual pre-labeled containers, and a biospecimen bag. Patients will collect fecal material in a collection container, and then transfer a pea size amount of fecal matter using the provided CultureSwabs, into the original pre-labeled fecal swab collection container, and place in the provided biospecimen bag. The patient will be asked to store the fecal samples in the freezer and deliver to the research site within 72 hours of collection (this will correspond with the patients' return to clinic - so it is not anticipated that additional clinic visits should be required).

6.1.6.1 *Withdrawal/Discontinuation*

When a patient discontinues/withdraws prior to trial completion, all applicable activities scheduled for the EOT visit should be performed at the time of discontinuation. Any adverse events which are present at the time of discontinuation/withdrawal should be followed in accordance with the safety requirements outlined in Section 6.2 - Assessing and Recording Adverse Events.

6.1.6.2 *Blinding/Unblinding*

This is a double-blind, randomized, placebo-controlled phase II trial with the identity of the treatment unknown to the patients, investigators and the Sponsor. Only the site pharmacist and unblinded trial monitor will be aware of the assigned treatment arm.

Investigators will be able to unblind in emergency situations when the identity of the treatment must be known in order to provide appropriate treatment. The sponsor must be contacted (if possible) prior to the treating investigator unblinding a patient.

Additionally, at the time of disease progression the treating investigator may request the unblinded treatment assignment for the patient. This will be provided by the unblinded trial monitor to the treating Investigator for the purposes of considering future treatment options. The remainder of the trial team will not have access to this unblinded treatment assignment.

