9.4 Confidentiality

The Investigator and any other personnel involved in this trial shall not disclose, or use for any purposes (other than for the performance of this trial any data, records, or other information (hereinafter collectively “information”) disclosed to the Investigator or other trial personnel. Such information shall remain the confidential and proprietary property of the TGen and SU2C, and shall be disclosed only to the Investigator or other designated trial personnel.

Patient confidentiality will be ensured by using assigned site-specific Screening and Randomization numbers (refer to Section 6.1) throughout the trial.

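### A fixed block size of 4, printed in the protocol, combined with release of arms at progression lets some blinded patients' arms be inferred, mainly at a high-enrolling site

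*Protocol*

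**What the plan says.** Protocol section 4.3 sets the allocation: "Randomization will be in a 1:1 ratio to pembrolizumab + paricalcitol or pembrolizumab + placebo", generated by a "computer-generated algorithm with a block size of 4". There is one list: "The unblinded monitor will provide the next randomized treatment from the sequence to the site pharmacist". Section 4.4 adds "No stratification will be performed", and section 4.1 plans 24 patients from up to 7 centres. The list is therefore six blocks of two plus two that run across sites.

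Section 6.1.6.2 (Blinding/Unblinding) provides that "at the time of disease progression the treating investigator may request the unblinded treatment assignment for the patient". The arm goes to that investigator only, and the rest of the trial team stays blinded. The same section takes a patient off trial medication once unblinded.

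On the site's records, section 6.1.1.7 says "This randomization number will be maintained on a Randomization log in the Investigator Site File", and section 9.4 speaks of "assigned site-specific Screening and Randomization numbers". No section says whether the number gives the position in the central list.

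Section 6.1.2.6 has each scan read by the investigator and, independently, by a central radiologist who does not know the arm.

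**The concern.** With a known block of two plus two, two patients of the same arm fix the other two. Releases at progression supply that information, and unevenly: the design expects 11/12 of controls but only 5/12 of combination patients to progress by 6 months. The arms released are mostly control arms, so the patients exposed are mostly combination patients without progression. They carry the primary comparison.

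The protocol treats knowledge of the arm as incompatible with staying on treatment. A patient whose arm is deduced from block-mates nevertheless stays on treatment and under assessment, and nothing would detect it. The investigator would still be reading scans, choosing whether to scan early (section 6.1.2.6) and deciding on withdrawal (section 4.8) with the arm in mind. While enrolment is open, the same knowledge helps to predict the next allocation. The direction of any resulting bias cannot be known in advance.

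**Working it through.** **1. The plan's own figure.** Section 8.2 states 90% power for 12 per arm, one-sided alpha 0.05, with the synopsis rates of 1/12 v 7/12 progression-free. Exact enumeration of the Pearson test gives 90.1%. The Miettinen-Nurminen score method gives 88.8% at 1/12 v 7/12 and 89.0% at 8% v 58% (stated: 89%). Both are reproduced, and this point does not affect them. The documents give no figure for how often an arm can be deduced.

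**2. Upper bound.** Assume that every progressor's arm is requested, block positions are known, and one person holds all released arms. A patient's arm is certain when both opposite-arm block-mates have been released:

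- progression-free combination patient: (11/12)² = 0.840
- progression-free control: (5/12)² = 0.174
- all progression-free patients (7 combination and 1 control expected): (7 × 0.840 + 1 × 0.174)/8 = 0.757, about 6 of 8

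**3. Own-site knowledge only.** Both block-mates must be at the same site. If that site has a share s of enrolment, multiply by s². The documents give no shares, so a range is shown. For fixed blocks of 6 and 8 the exponent 2 becomes 3 and 4.

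| Knowledge | Block 4 | Block 6 | Block 8 |
|---|---|---|---|
| All released arms | 76% | 68% | 62% |
| Own site, s = 1/7 | 1.5% | 0.2% | 0.03% |
| Own site, s = 1/6 | 2.1% | 0.3% | 0.05% |
| Own site, s = 1/3 | 8.4% | 2.5% | 0.8% |
| Own site, s = 1/2 | 19% | 8.5% | 3.9% |

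For example, at s = 1/2 with blocks of 4: 0.25 × 0.757 = 0.189.

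**4. Chance of at least one certain own-site deduction in the trial** (simulation, 24 patients in six blocks): 10-12% with seven equal sites, 15% with six, about 52% if one site enrols half, and about 86% if one site enrols 70%.

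**5. Timing.** Steps 2 to 4 count all progression by 6 months. Scans fall at about weeks 9, 18 and 27, and week 27 is day 189, after the day-180 endpoint. With simultaneous entry and a constant hazard (an assumption), the share of controls released by week 18 is 1 − (1/12)^(18/26) = 82%, and 0.82² = 67% replaces 84%. With uniform accrual over one, two or three years, the simulated 76% falls to about 65%, 60% and 55% when only releases before the patient's own day 180 count.

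**6. Partial knowledge.** One released block-mate leaves three patients, two of them in the opposite arm, so a guess moves from 1/2 to 2/3. This applies only if the investigator knows that the two patients share a block.

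**7. Leverage of one patient.** By the one-sided Pearson test, 5/12 v 1/12 progression-free gives z = 1.886, p = 0.030. For 4/12 v 1/12, z = 1.508, p = 0.066.

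**The case against.** The strongest reply is that the pieces rarely meet. Blocks run across up to 7 centres, each arm goes only to that patient's investigator and only on request, and an investigator who cannot place patients in the central list does not know who shares a block. With equal sites the figure is 1.5-2%. Scan timing lowers it further. Section 6.1.2.6 also puts a blinded reader on every scan and requires central review of investigator-called progression before treatment stops. The SAP's Table 2 reports progression-free survival by independent assessment.

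Most of this stands, and it sets the size of the point. A reader might also infer from section 6.1.1.7 that the site log reveals the allocation order of the central list. The documents do not support that: the log sentence says only where the number is kept, section 9.4 calls the numbers site-specific, and any site already knows its own enrolment order from dates. The weight rests on sections 4.3 and 6.1.6.2.

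Two things remain. Neither Protocol section 8.3.4 nor SAP section 7.1 says which read decides the primary endpoint, so the blinded read is not an assured safeguard. A central read also does not control early scanning or withdrawal, and SAP section 7.1 excludes patients who are unevaluable at 6 months for a non-progression reason, so withdrawals can change the denominator.

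**Conclusion.** The weakness is real, limited and cheap to reduce. The fixed, disclosed block with release at progression allows certain deduction of some arms, mainly at a site that fills most of a block or if investigators share released arms. On own-site knowledge it affects about 1.5-2% of progression-free patients with six or seven equal sites, and about 19% of those at a site with half of enrolment. This assumes design progression rates, every arm requested and block positions known. The site shares are assumed.

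A reader might take 84% as the expected extent, and conclude that progression-free patients are generally unblinded. The documents do not support that. The 84% (17% for controls) requires one person to know every released arm and every block position, in time to matter. Nor is there any effect on the stated sample size or power.

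**What to change.** For allocations not yet made, use permuted blocks of randomly varying size, for example 2, 4 and 6, arranged to end at 12:12. Remove the block size from section 4.3, and keep the sizes in a document held by the trial biostatistician and the unblinded monitor. With unknown boundaries, certain deductions are in general no longer available. A larger fixed block would not achieve this: with all released arms known, 68% or 62% would still be deducible at block size 6 or 8. It would also help to state which read is primary.

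The cost is regenerating the unused part of the list and editing section 4.3. The temporary imbalance is at most 3 patients, against 2 now; sample size is unchanged. Final balance is kept apart from replacements under section 4.9, which can disturb it under either scheme. Patients already allocated are not helped: the SAP of July 2020 cites a November 2019 safety report, so enrolment had begun, and the number of allocations left is not stated.

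A single 12:12 list is not a good substitute, because its temporary imbalance can reach 12. Renumbering patients would add little, because a site knows its own enrolment order anyway.
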